#### **Bright Outcome Platform**

#### **Bright Outcome "Discussion" Feature**

Participants accessing the "Online Lessons" on the platform will have a tab called "Discussion" where they can discuss topics related to the study. These topics will be based on the Skills. For example, there will be a discussion thread called "Gratitude" so that participants can post there about their comments/thoughts on practicing gratitude. The discussion threads will be moderated by a staff member on the research team. The moderator will post weekly prompts to generate discussion, moderate the discussions to stay on-topic, and address and respond to any signs of distress or suicidal ideation. All posts will be tied to a SAGE LEAF Study ID and an avatar. No identifiable information will be posted/shared. Guidelines will include refraining from posting personal/identifiable information such as names and contact information, and refraining from bullying or using harsh/offensive language online. We have prepared a data safety and monitoring plan for the Discussion posts (in addition to a plan for handling a range of distress revealed to us at any point in the study), based on our previous online studies with an online forum such as LEAF, MARIGOLD, and LARKSPUR. (See Section **17.0 Data Monitoring Plan to Ensure Safety of Participants** for more details.)

#### **Profile Page**

Г

Participants will have access to a profile page where they will be able to select an avatar and fill out additional profile information (e.g. hobbies, challenges that they are facing as a caregiver, etc.) that they have the option of displaying if they choose to do so. No identifiable information will be posted/shared.

#### Virtual Awards Feature

Participants accessing the "Online Lessons" on the platform will have a page called "Awards" where they will receive virtual badges for reaching certain goals e.g. logging in daily for 7 days, completing home practice for 4 consecutive days, or completing an online module. They will also be able to view their achievements in relation to others. This data will also be collected on Bright Outcome. Each participant will be able to see their earned badges as an incentive to proceed and engage with the study.

#### **SAGE LEAF Positive Emotion Skills**

Please see the table below for an overview of the intervention's skills, goals, and home practice exercises, administered via the Bright Outcome online platform.

The total time involved from the beginning to the end of the study is approximately	y 8
weeks.	

Overview of Intervention sessions, Goals, and Home Practice.			
Skills	Goals of session	Home Practice	
Session 1: Positive Events, Savoring, Gratitude	Recognize positive events and the associated positive emotion; practice ways to amplify the experience of positive events; and learning to practice gratitude.	Noting a positive event each day and writing about it (savoring); starting a daily gratitude journal and daily emotion reports. The gratitude list home practice continues through the rest of the intervention period.	
Session 2: Everyday Mindfulness and Mindfulness Meditation	Learn and practice the awareness and nonjudgment components of mindfulness.	Daily informal mindfulness activities, a 10-minute formal breath awareness activity, continuing the gratitude journal and daily emotion reports.	
Session 3: Positive Reappraisal	Understanding positive reappraisal and the idea that different forms of positive reappraisal can all lead to increased positive emotion in the face of stress.	Reporting a relatively minor stressor each day, then listing ways in which the event can be positively reappraised. The daily formal mindfulness practice, gratitude journal, and	

		the emotion reports continue.
Session 4: Self-Compassion	Participant learns about how to show compassion for the self, especially in the context of a caregiver. Understanding how self-compassion relates to the skills throughout the rest of the SAGE LEAF course.	Listing an act of self- compassion for each day. The 10-minute mindful breathing, gratitude journal, and daily emotion reports continue.
Session 5: Personal Strengths, Attainable Goals	Participant lists his or her personal strengths and notes how they may have used these strengths recently; understanding characteristics of attainable goals and setting some goals for the week.	Listing a strength each day and how it was "expressed" behaviorally, working toward one of the attainable goals, and noting progress each day. The 10-minute mindful breathing, the gratitude journal, and the daily emotion reports continue.
Session 6: Skills Summary	Participants will receive a summary of the SAGE LEAF course as a whole. Participants will identify which skills they enjoyed or did not enjoy and why. They will make a plan to practice the positive emotion skills beyond the SAGE LEAF course.	Course wrap-up. The 10- minute mindful breathing, the gratitude journal, and the daily emotion reports continue.
Catch-Up Week	No new skills introduced. Participants continue with daily emotion reports and catch up on any home practice exercises.	Daily emotion reports continue.
Catch-Up Week	No new skills introduced. Participants continue with daily emotion reports and catch up on any home practice exercises.	Daily emotion reports continue.

#### Measures

Participants will complete self-report questionnaires at 2 time points over approximately 8 weeks. The assessments will be named by their time point "T", e.g. T1 (baseline) and T2 (approx. 6-8 weeks from baseline). At T3 (8 weeks from baseline), participants will participate in a 45-60 min feedback interview (see attached interview guide) through videoconferencing with a member of the study team. All self-report assessments will be completed from home via tablet, a home computer, or mobile device. All instruments will be uploaded to this application for NU IRB approval. In addition to the self-report measures (listed below), we will also assess the following demographic variables, including age, gender, and race/ethnicity. We will assess the following self-report measures in each assessment:

#### Table of Measures

	Full Name of Measure	Administered at:	In reference to:
1	Demographics (see uploaded instruments)	Baseline (T1) only	
2	Technology Survey	Baseline (T1) only	Technology/Usability
3	System Usability Scale (SUS)	T2	Technology/Usability
4	Perceived Usefulness Scale (PSU)	T2	Technology/Usability

5	Technology Acceptance Model (TAM)	T2	Technology/Usability
6	Recommendations & Skill Use	T2	Technology/Usability
7	Zarit Burden Interview	All timepoints	Psychological
			Adjustment
8	Oberst Caregiving Burden Scale	All timepoints	Psychological
	(OCBS)		Adjustment
9	Positive Aspects of Caregiving Scale	All timepoints	Psychological
			Adjustment
10	Caregiver reaction assessment	All timepoints	Psychological
			Adjustment
11	Caregiving Mastery subscale of the	All timepoints	Psychological
	Caregiving Appraisal Measure		Adjustment
12	Loneliness/social isolation	All timepoints	Psychological
			Adjustment
13	Psychological wellbeing (NIH Toolbox)	All timepoints	Health Behaviors
14	PROMIS measures (anxiety,	All timepoints	Psychological
	depression, perceived stress, life		Adjustment
	satisfaction, self-efficacy, and meaning		
	and purpose)		
15	Cohen's perceived stress scale	All timepoints	Psychological
			Adjustment
16	Differential Emotions Scale	Daily Throughout	Psychological
		Intervention	Adjustment

#### Procedures for Phase 2: Pilot Test

Upon providing informed consent and completing the phone screen, consented individuals will then be provided access to the SAGE LEAF platform through a sign-up email prompting them to set up their password.

#### 6 Sessions over 8 weeks: approx. 30 minutes/online module

The format and content of the SAGE LEAF pilot test will be the same as the user test. The same online platform will also be used, with minor refinements made based on feedback from the user tests.

#### Time Commitment

The estimated time commitment for participating in the SAGE LEAF Study is up to 15 hours over 8 weeks.

Event	Time
	Commitment
Screener + Phone Screen + Consent + 2 surveys (up to 1 hour each)	~7 hours
6 SAGE LEAF Sessions	<3 hours
Daily Home Practice / Emotion Check-In	~3 hours
Feedback Survey + Interview	<2 hours
Total Hours Over 8 Weeks	<15 hours

#### Measures

Participants will complete self-report questionnaires at 2 time points over approximately 8 weeks. The assessments will be named by their time point "T", e.g. T1 (baseline) and T2 (approx. 6-8 weeks from baseline). At T3 (8 weeks from baseline), participants will participate in a 45-60 min feedback interview (see attached interview guide) through videoconferencing with a member of the study team. All self-report assessments will be completed from home via tablet, a home computer, or mobile device. All instruments will be uploaded to this application for NU IRB approval. In addition to the self-report measures (listed below), we will also assess the following demographic variables, including age, gender, and race/ethnicity. We will assess the following self-report measures in each assessment:

	Full Name of Measure	Administered at:	In reference to:
1	Demographics (see uploaded	Baseline (T1) only	
	instruments)		
2	Technology Survey	Baseline (T1) only	Technology/Usability
3	System Usability Scale (SUS)	T2	Technology/Usability
4	Perceived Usefulness Scale (PSU)	T2	Technology/Usability
5	Technology Acceptance Model (TAM)	T2	Technology/Usability
6	Recommendations & Skill Use	T2	Technology/Usability
7	Zarit Burden Interview	All timepoints	Psychological
			Adjustment
8	Oberst Caregiving Burden Scale	All timepoints	Psychological
	(OCBS)		Adjustment
9	Positive Aspects of Caregiving Scale	All timepoints	Psychological
			Adjustment
10	Caregiver reaction assessment	All timepoints	Psychological
			Adjustment
11	Caregiving Mastery subscale of the	All timepoints	Psychological
	Caregiving Appraisal Measure		Adjustment
12	Loneliness/social isolation	All timepoints	Psychological
			Adjustment
13	Psychological wellbeing (NIH Toolbox)	All timepoints	Health Behaviors
14	PROMIS measures (anxiety,	All timepoints	Psychological
	depression, perceived stress, life		Adjustment
	satisfaction, self-efficacy, and meaning		
	and purpose)		
15	Cohen's perceived stress scale	All timepoints	Psychological
			Adjustment
16	Differential Emotions Scale	Daily Throughout	Psychological
		Intervention	Adjustment

#### **Table of Measures**

#### 9.0 Research with Vulnerable Populations

This research does not involve the vulnerable populations indicated.

## **10.0** Incomplete Disclosure or Deception:

N/A

## **11.0** Consent Process:

For both phases, online consent will take place through a REDCap electronic consent form. Consent will be time-stamped and participants will be able to save, download, and/or print a copy of the consent form for their records. Participants will consent electronically by entering the date and by typing their full name into the form, which will represent their electronic signature. Participants will be considered "consented" only if they provide both items (date and electronic signature). Participants may also email the project director to request a copy of the consent form at any time.

If a participant chooses to withdraw during the study, their data will be retained up until their point of withdrawal. When a participant withdraws, they will no longer receive future assessments and they will no longer receive daily reminders to log-in to the website. Participants can consent to be contacted for future studies. They can also consent to receive SMS text messages to receive their survey assessments. Please refer to the consent form. Study staff will monitor the REDCap project daily in order to track any new completed consent documents and update study tracker.

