Next, we will conduct a (N=30) single-arm pre-post 2) **pilot test / feasibility study** of SAGE LEAF for AD caregivers. Participants will receive access to the SAGE LEAF platform and complete the positive emotion skills intervention over 6 weeks. We will evaluate the number and percentage of participants retained at the post assessment as well as the means and ranges for the proportion of intervention content completed (i.e., number of pages viewed out of the total possible pages across all skills and lessons in the intervention) and participants' acceptability ratings (i.e., participants' ratings of whether they would recommend SAGE LEAF to other AD caregivers).

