#### Withdrawal of participants

If a participant wishes to withdraw, he/she can communicate this on the phone or via email to the project director. Study staff will also be monitoring communications and potentially withdrawal requests coming through on the study website or study email. The participant will then be promptly withdrawn from the study, their data collected and eventually analyzed only up until the point of withdrawal. No further data will be collected after a participant has been withdrawn. We will document the reason for withdrawing.

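### Withdrawal is the only participant-initiated exit described and it ends T2 and the interview, so caregivers withdrawn before T2 give no usability, usefulness or acceptability rating

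*Combined protocol and SAP*

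**What the plan says.** Two places govern leaving the study.

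- **Section 11.0, Consent Process:** "When a participant withdraws, they will no longer receive future assessments", and the daily log-in reminders stop as well. Data gathered before that point are retained.
- **Section 17.0, Withdrawal of participants:** "If a participant wishes to withdraw, he/she can communicate this on the phone or via email to the project director". Staff also watch the study website and email for such requests. The consequence is "The participant will then be promptly withdrawn from the study", and then "No further data will be collected after a participant has been withdrawn". One further item is kept: "We will document the reason for withdrawing".

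The outcomes that depend on these rules are set elsewhere.

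- **Section 1.0** on retention in the pilot: "We will evaluate the number and percentage of participants retained at the post assessment". The denominator is not written out. The same paragraph plans means and ranges for content completion and for the rating of whether participants would recommend the programme.
- **Section 8.0, Measures (both phases):** SUS, perceived usefulness, TAM and "Recommendations & Skill Use" are listed at T2 only. The feedback interview is at T3.
- **Section 22.0:** usability, usefulness, feasibility and acceptability are the primary measures, summarised by medians and interquartile ranges. Handling of missing T2 data is not described.

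**The concern.** The study asks whether caregivers find the platform usable, useful and acceptable, and whether they stay. Section 1.0 itself notes that self-guided programmes suffer high attrition and poor adherence. People who leave because the platform is hard to use or unhelpful are among the most informative respondents. Under the written rule their withdrawal removes the T2 ratings and the interview in one step. In the user test, the end-of-programme surveys and interviews feed the refinement of the platform, so the structured part of their feedback is lost there too.

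The text gives staff only one category to apply. No step asks whether a caregiver who makes contact wants to stop the lessons or wants to stop giving data. Two caregivers with the same platform use could then be treated differently. One makes contact, is recorded as withdrawn and is not sent T2. The other stops logging in, is not withdrawn under any stated rule, and counts as retained if T2 is answered.

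**Working it through.** The plan gives no attrition, retention or precision figure to reproduce. Its sample sizes add up (20 + 30 = 50, Section 3.0). The check has two parts.

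**1. What exists for a caregiver withdrawn before T2**

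| Item | Where set | Available? |
|---|---|---|
| Log-ins, exercises, skills completed, daily emotion reports, posts | 8.0, kept under 11.0 | Yes, up to withdrawal |
| Feedback submitted for lessons | 18.0, kept under 11.0 | Yes, up to withdrawal |
| Content completion | 1.0 | Yes, up to withdrawal |
| Reason for leaving | 17.0 | Yes |
| SUS, usefulness, TAM, recommendation item | 8.0, T2 only | No |
| Feedback interview | 8.0, T3 only | No |

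Three of the four primary constructs in Section 22.0 (usability, usefulness, acceptability) lose their rating. Feasibility is partly preserved through content completion.

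**2. Scale, with assumed counts**

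*Bounds.* Take N = 30, with w withdrawn before T2. Everyone else answers T2, and x of them recommend (about 90%, rounded). The rate among responders is x/(30 − w). The rate among all enrolled lies between x/30 (no leaver would recommend) and (x + w)/30 (every leaver would), so the width is w/30.

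| w | T2 n | x | Among responders | All-enrolled bounds | Retention |
|---|---|---|---|---|---|
| 3 (10%) | 27 | 24 | 88.9% | 80.0% to 90.0% | 90% |
| 6 (20%) | 24 | 22 | 91.7% | 73.3% to 93.3% | 80% |
| 9 (30%) | 21 | 19 | 90.5% | 63.3% to 93.3% | 70% |
| 12 (40%) | 18 | 16 | 88.9% | 53.3% to 93.3% | 60% |

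*Offering T2 to those who stop only the course.* Start from the w = 6 row. Suppose k of the 6 would have answered T2 if asked, and r of those k would recommend. Retention becomes (24 + k)/30 and the recommendation rate (22 + r)/(24 + k).

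| k | r | Retention | Recommend |
|---|---|---|---|
| 0 | 0 | 24/30 = 80.0% | 22/24 = 91.7% |
| 1 | 0 | 25/30 = 83.3% | 22/25 = 88.0% |
| 1 | 1 | 25/30 = 83.3% | 23/25 = 92.0% |
| 4 | 0 | 28/30 = 93.3% | 22/28 = 78.6% |
| 4 | 2 | 28/30 = 93.3% | 24/28 = 85.7% |
| 4 | 4 | 28/30 = 93.3% | 26/28 = 92.9% |

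With k = 4, retention rises by 13.3 points whatever r is. The recommendation rate falls by 13.1 points (r = 0) or 6.0 points (r = 2), or rises by 1.2 points (r = 4).

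*Planned summaries.* A percentage recommending is not the planned statistic. In the case k = 4, r = 0, 6 of 28 ratings fall below recommending. The median (between the 14th and 15th ordered values) stays in the recommending group, and so does the lower quartile (7th and 8th ordered values). The mean and the low end of the range, planned in Section 1.0, are the summaries that can move.

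**The case against.** The strongest reply is that ending data collection when someone withdraws from a study is an ordinary protection. In exploratory single-arm work with N=20 and N=30, missing ratings from early leavers are a limitation that can simply be reported. There is no between-arm comparison to bias. That is fair as far as it goes. It does not explain why the documents lack a lesser option for someone willing to keep answering questions, when ratings from such people are what the study is for.

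Four stronger readings are tempting, and the documents do not support them.

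- **That anyone who tells staff they are stopping the lessons is automatically withdrawn and denied T2.** Sections 11.0 and 17.0 apply to someone who chooses or wishes to withdraw. Extending them to a caregiver who only stops the lessons is a reading of silence. Section 19.0 lets participants skip exercises or questions while enrolled, and no text withdraws those who stop logging in.
- **That only the reason for leaving survives.** Usage data, lesson feedback and posts made earlier are kept.
- **That retention describes mainly those who stayed.** Retention counts who stayed, so withdrawn participants lower it if the denominator is all enrolled. Its weakness is that it mixes two different events.
- **That withdrawal is the only exit of any kind.** Section 19.0 also allows the investigator to release a participant.

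The consent form and phone script are not in the text reviewed and may draw the distinction. If they do, Sections 11.0 and 17.0 should be brought into line with them.

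**Conclusion.** The concern holds as a gap in the data-collection rule. The only participant-initiated exit described ends reminders, T2 and T3 together, and no course-only status is defined. A caregiver handled as withdrawn before T2 is therefore missing from the usability, usefulness and acceptability ratings and from the interview.

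An upward bias in those ratings follows only if such leavers are less satisfied than those who stay. That is plausible, but the documents do not establish it. If they left for reasons unrelated to the platform, the ratings may hardly change. Retention may understate willingness to be assessed, because it cannot tell stopping the course from leaving the study.

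The size cannot be fixed without an attrition rate. Under the assumed 10% to 40% withdrawn, the recommendation rate among all enrolled is undetermined over 10 to 40 percentage points. A median would be less sensitive than a mean or a range. The change is worth making before enrolment, because ratings that were never requested cannot be recovered in analysis.

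**What to change.** Amend Sections 11.0 and 17.0, with matching consent wording, to define two statuses:

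- **(a) Stops the course.** Lesson reminders cease. T2 (at minimum SUS, usefulness and the recommendation item) and the T3 interview are still offered unless the participant declines.
- **(b) Withdraws from further data collection.** Nothing more is collected, as now.

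Staff ask which applies and record status, date and reason. In Sections 1.0 and 22.0, state that course discontinuation and T2 completion are reported as two separate percentages of all enrolled. Show every T2 rating with the number responding beside the number enrolled.

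The cost is a few sentences, one tracker field and one extra question to someone who is leaving. There would also be a few more survey links and incentives, within the $50 per participant already planned in Section 14.0 ($20 + $30). The right to leave entirely is unchanged.

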## **12.0** Waiver of Participant Signature on Consent Form:

N/A

## **13.0** Waivers and Alterations of Consent Information:

N/A

## 14.0 Financial Compensation:

For both phases of the study, SAGE LEAF participants will receive escalating incentives in the form of e-gift cards: \$20 for the completion of both assessments at T1 and T2; \$30 for the feedback interview for a total of \$50 per participant.

## 15.0 Audio/Video Recording/Photography

Our sources of research material include the video recordings from the feedback interviews that will be conducted through Zoom videoconferencing. Once the video files

have been transferred and saved to the MSS server (identified only by StudyID), these video files will be transcribed with identifying information removed, and the video files will be permanently deleted.

## **16.0** Potential Benefits of this Research:

There is no guaranteed benefit from participating in SAGE LEAF, however participants might enjoy the skills taught and continue practicing them beyond the online course e.g. keeping a gratitude journal, completing everyday chores mindfully, or listening to a breath awareness meditation recording. Participants may gain mindfulness skills, regularly capitalize on positive events, or use positive reappraisal to reassess daily stressors. Even after completing the course, participants are encouraged to keep using their favorite skills, whether formally through the website and/or journaling about their experiences, or informally in their everyday lives.

On a broader scale, we predict that the skills taught in SAGE LEAF may help AD caregivers increase their positive affect and lower depression, anxiety, caregiver burden, and perceived stress.

## **17.0** Potential Risks to Participants:

#### Minimal Risk; Possible discomfort while interacting with the SAGE LEAF platform

SAGE LEAF is relatively easy to administer and is a low cost intervention compared to existing interventions. A potential risk of discomfort might arise with participants who have less experience using the internet, a tablet/computer, or mobile device. Participants might experience frustration or delayed onboarding if they are less familiar with using computer applications, browsing the internet, or connecting to wireless internet. All participants will receive clear instructions for website/technology use, and guidance on how to use the hardware/software required to participate in the study to ensure lack of online experience is not a barrier to participation.

